8.4 Assessments – in-clinic

All study procedures will be performed at the local physiotherapy practices, by the treating physiotherapist, with coordination with Radboudumc. Physiotherapists will be extensively trained in performing all assessments as part of the study protocol in a highly standardized manner. They will also be guided and coached by the research team at Radboudumc to increase engagement and data quality. Participants are invited to come to the study site four times over a 15 week duration. The in-clinic assessments consist of a number of walking tests: 6MWT (twice), TUG (twice), and 10MWT with and without cognitive load (three times for each context). In addition, demographics are taken during the first visit and participants are asked to fill out some questionnaires on disease symptoms and quality of life after each study visit. Questionnaires can be filled out digitally at home or at the physiotherapy practice if the participant does not own a computer. The exact assessments are described in Table 2 (in-clinic and at-home assessments).

8.5 Assessments – at-home

After the first study visit to physiotherapists' clinics, participants will be asked to wear the Study Watch (up to 23 hours a day) for passive longitudinal measurements of physiologic activity and environmental data. In addition, all participants will be asked to complete the virtual 6MWT with pre- and post-6MWT Borg Scales and virtual TUG, once a week (every week on the same day) with guidance via graphical user interface on the Study Watch. The Verily Study Watch will provide an alert to the participant at 9 am of the preset day of the week (preset during the first visit by site coordinator) to remind them to perform the task. Participants with PD will be asked to perform the Walk Test 30 minutes to an hour after they intake medication and tag the event on the Study Watch. Participants with COPD are asked to perform the task any time they prefer during the day that they receive an alert on the Study Watch. Participants will have the ability to postpone the task until a later time point in the same day, should that suit their schedule better. If a prescribed task is not executed on a given day, the reminder alert will be prompted the next day at 9 am. Participants with PD are also asked to tag time of medication intake every time they intake PD medication.

Participants with COPD are not asked to tag time of medication intake. Figure 3 describes the in-clinic and at-home sequences of assessments using the Study Watch. Participants will also wear the Modus StepWatch 4 concurrently with the Study Watch over 14 days, which can fall on any random 10 days with a minimum of two weekend days. At least four to six hours of wear on these days is intended.

A subset of participants may also wear the Fitbit Sense concurrently with the Study Watch and will be asked to wear them for the first 5 weeks between first and second visits.

Figure 3. Study Watch Assessment Sequences in clinic and at home.

FW/UX user journey

In-clinic (three types of walk tasks & PD-only UPDRS in one day)

At-home (two types of walk tasks in one day)

Each box is a task guided by the Study Watch graphical user interface. Different hues of gray represent three different types of walk tasks and 2-minute rest periods. Dotted boxes indicate activities required only for the participants with PD. In-clinic: dotted box indicates in-clinic MDS-UPDRS part III that we will indicate start and finish of the subtests using the Study Watch. At-home: during at-home periods, participants with PD will be asked to tag medication intake whenever they take medications. For the prescribed day of the week, participants will receive an alert from the watch. Participants with PD will be instructed to perform Virtual Walk Test within 30 min to an hour relative to a medication intake on that day. Participants with COPD will be instructed to perform the task any time they prefer during the prescribed, alerted day.

8.6 Timeline

We aim to include 300 participants within 18 months. We will include 25 – 30 physiotherapy practices with both a ParkinsonNet physiotherapist and a physiotherapist specializing in COPD (up to 50 physiotherapists). On average each ParkinsonNet physiotherapist³⁰⁻³² will need to include 4 PD participants and each therapist specializing in COPD should include 8 COPD participants. This breaks down into 1 participant with PD per physiotherapist per 2 months and 1 participant with COPD per physiotherapist per month. Based on our extensive experience in performing large clinical trials,^{5,33-37} we expect this to be highly feasible. After 3 months of inclusion, if we find that enrollment rates are too low, we have an alternative, backup scenario in place in which we will recruit participants with COPD from hospitals that have a high case load of people with COPD or with PD (either pulmonologists or neurologists). In this case, outpatient clinics will refer people with COPD to selected COPD specialized physiotherapists and the study activities will be performed as planned. With 15 weeks follow-up, all data should be included 13 months after first enrollment.

8.7 Withdrawal of individual subjects

Participants can leave the study at any time for any reason if they wish to do so without any consequences. The investigator can decide to withdraw a subject from the study for urgent medical reasons. If a subject at any time discontinues involvement in the study for any reason (drops-out) without explicitly withdrawing consent, the subject will be considered to only have participated in the portion of the study with which he/she was eligible and present. The subject will be considered a "non-participant" for the portion of the study for which he/she was not eligible or not present. The scope of the information covered in the informed consent is limited only to the data collected while

the subject is actively participating in study.

8.8 Specific criteria for withdrawal (if applicable)

Participants will only be withdrawn from the study when a medical condition does not allow the participant to continue the study procedures, e.g. because of repeated falling or an unstable cardiovascular condition. In case of a (serious) adverse event, the sponsor will carefully evaluate whether the participant can continue to participate in the study (see section 9.2 on adverse events).

Participants that, during the study, turn out to not have either COPD or PD, but another related diagnosed (i.e. Parkinsonism) will be withdrawn from the study.

8.9 Replacement of individual subjects after withdrawal

We have taken into account 25% of data loss due to a drop-out or any other reasons in our sample size calculation of the COPD cohort. If the COPD cohort encounters higher than 25% drop-out rates, we will include new participants until we reach 150 complete COPD cases. For the PD cohort we have considered 10% drop-out. If the PD cohort exceeds the 10%, we will include new participants until we reach 90 complete PD cases.

8.9 Follow-up of subjects withdrawn from treatment

If a subject at any time chooses to withdraw from the study, further attempts to collect data will not be undertaken.

If a subject at any time discontinues involvement in the study for any reason (drops-out), the subject will be considered to only have participated in the portion of the study with which he/she was eligible and present. The subject will be considered a “non-participant” for the portion of the study for which he/she was not eligible or not present.

8.10 Lost-to- Follow-up

A subject will be considered lost-to-follow-up and terminated from the study when three unsuccessful attempts by the Investigator or his/her designee to contact the subject have been documented.

8.11 Premature termination of the study

If suspicion of an unacceptable risk to subjects arises during the clinical investigation, or when so instructed by the Ethics Committee (EC), the sponsor shall suspend the clinical investigation while the risk is assessed. The sponsor shall terminate the clinical investigation if an unacceptable risk is confirmed. Moreover, the sponsor will consider terminating or suspending the participation of an Investigator if monitoring and/or auditing identifies major or repeated deviations on the part of an Investigator.

8.12 Potential factors impacting the data collected

We designed the study to mitigate potential factors affecting data quality and sources of bias.

The main factors considered were participant compliance (requirement to wear the Study Watch for the duration of the study), fatigue bias (when participants repeat tests during sessions), and learning bias (associated with surveys).

Study Watch wear compliance will be monitored and controlled. Physiotherapists will be notified if participants are not compliant and will discuss with participants at the following visit.

Fatigue bias will be monitored by surveys(Facit and Epworth) and assessed by the physiotherapists during clinic visits who may offer breaks.

Learning bias will be mitigated by analyzing the data controlling for the number of repetition of the survey.

Factors associated with participant compliance.

Wearing the Study Watch for the duration of the study is essential for data quality. We will be collecting the daily wear of the Study Watch by participants and control the collected data for compliance. Physiotherapists will be notified

9. SAFETY REPORTING

9.1 Temporary halt for reasons of subject safety

In accordance with section 10, subsection 4, of the WMO (Medical Research Involving Human Subjects Act; in Dutch: Wet Medisch-wetenschappelijk Onderzoek met Mensen), the sponsor will suspend the study if there is sufficient ground that continuation of the study will jeopardise subject health or safety. The sponsor will notify the accredited METC (Medical research ethics committee (MREC); in Dutch: medisch-ethische toetsingscommissie (METC)) without undue delay of a temporary halt including the reason for such an action. The study will be suspended pending a further positive decision by the accredited METC. The investigator will take care that all subjects are kept informed.

9.2 AEs, SAEs, ADEs, SADEs, and device deficiencies

9.2.1 Adverse events (AEs) and Adverse device effect (ADE)

Adverse events are defined as any undesirable experience occurring to a subject during the study, whether or not considered related to the investigational product or any trial procedures. All adverse events reported spontaneously by the subject or observed by the investigator or his/her staff will be recorded. Adverse events will be classified according to the definition in Table 3.

An Adverse Device Effect (ADE) is an adverse event related to the use of an investigational medical device. Note that this definition includes any adverse event resulting from insufficiencies or inadequacies in the instructions for use, the deployment, the implantation, the installation, the operation, or any malfunction of the investigational medical device. That also includes any event that is a result of a use error or intentional abnormal use of the investigational medical device.

Table 3. Adverse event (AE) classification

ADVERSE EVENTS	Non-device-related	Device- or procedure related
Non-Serious	Adverse Events (AE)	Adverse Device Effect (ADE)
Serious	Serious Adverse Event (SAE)	Serious Adverse Device Effect (SADE) Unanticipated Serious Device Effect (USADE)

No AEs are expected from the clinical assessments of the self-reported questionnaires.

AEs that may be expected from the Verily Study Watch, include: pruritus, dryness, redness, rash, and swelling around the wrist from wearing of the Study Watch. Participants exhibiting anticipated adverse events related to Study Watch shall contact the Radboud study team and discuss whether they can continue to participate in the study.

Any pre-existing medical condition or symptom present in a subject will not be considered an AE in this study, unless it worsens as a result of this study. Any mild changes that occur will be monitored by the Investigator and data will be recorded appropriately.

9.2.2 Serious adverse events (SAEs) and serious adverse device effect (SADEs)

A serious adverse event is any untoward medical occurrence or effect that:

- Results in death;
- Is life threatening (at the time of the event);
- Requires hospitalization or prolongation of existing inpatients' hospitalization;
- Results in persistent or significant disability or incapacity;
- Is a congenital anomaly or birth defect; or
- Any other important medical event that did not result in any of the outcomes listed above due to medical or surgical intervention but could have been based upon appropriate judgment by the investigator.

In accordance with section 10, subsection 1, of the WMO, the investigator will inform the subjects and the reviewing accredited METC if the frequency and severity of adverse effect suggests that the disadvantages of participation may be significantly greater than what was foreseen in the protocol. The study will be suspended pending further review by the accredited METC, except insofar as suspension would jeopardize the subjects' health. The investigator will ensure that all subjects are kept informed.

The following hospitalizations are not considered to be an SAE:

- Hospitalizations due to PD or COPD; or
- Hospital admissions that already were scheduled at the moment of inclusion.

The sponsor will report the SAEs through the web portal, ToetsingOnline, to the accredited METC that approved the protocol, within seven (7) days of first knowledge for SAEs that result in death or are life threatening followed by a maximum period of 8 days to complete the initial preliminary report. All other SAEs will be reported within a maximum period of 15 days after the sponsor has first knowledge of the serious adverse events. SAEs will also be reported in the annual progress report to the accredited METC, until the end of the study in the Netherlands.

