9.5 Data Safety Monitoring Board (DSMB) / Safety Committee

We will not install a DSMB as this study includes limited risks (see section 12).

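### Section 9.2.2 exempts PD and COPD admissions from SAE status with no exception for worsening caused by the study, in conflict with 9.2.1 and leaving SADEs unclear

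*Combined protocol and SAP*

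**What the plan says.** Section 9.2.2 lists the criteria that make an event serious. One is hospitalisation ("Requires hospitalization or prolongation of existing" inpatient stay). Others are death, a threat to life, lasting disability and other important medical events. The section then says "The following hospitalizations are not considered to be an SAE" and names two kinds: "Hospitalizations due to PD or COPD", and admissions already planned at inclusion. The first carries no condition on cause, and the words 'due to' are not defined.

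Section 9.2.1 deals with pre-existing conditions. They are not adverse events (AEs) "unless it worsens as a result of this study". Table 3 in the same section classifies events by seriousness and relatedness. SAE is the label for serious events not related to the device; serious events related to the device or a procedure are labelled SADE.

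In 9.2.2 the METC receives reports within 7 days for fatal or life-threatening SAEs and within 15 days for all other SAEs. SAEs are also listed in the annual progress report. Separately, the METC and participants are informed, and the study is suspended pending review, "if the frequency and severity of adverse effect suggests that the disadvantages of participation may be significantly greater" than foreseen. Section 9.5 states: "We will not install a DSMB as this study includes limited risks".

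**The concern.** The study adds a procedure that these patients would not otherwise undergo: a weekly unsupervised 6-minute walk test and Timed Up and Go test at home (section 8.5). If such a test sets off a COPD exacerbation or a worsening of PD that leads to admission, that is the type of event that prompt reporting exists to show. The exemption as worded does not separate such an admission from one that reflects the natural course of the disease.

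The two adjoining sections also run in opposite directions. The causal exception is present for the AE, the lower tier, and missing for the SAE, the higher one. With no DSMB, expedited METC reports are a main route by which someone outside the study team would see a provoked admission soon after it happens.

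**Working it through.** The point concerns a definition, and the plan has no figure to reproduce. The check is to follow one case through the text: a participant whose COPD or PD worsens because of a home walk test and who is admitted, but whose event is not fatal, life-threatening or disabling and is not otherwise judged an important medical event.

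1. **AE status (9.2.1).** The condition was pre-existing but worsened because of the study, so the causal exception applies and the event is a recordable AE.
2. **Relatedness (Table 3).** AEs are classified by this table, so the event belongs in the device- or procedure-related column.
3. **Seriousness (9.2.2).** Admission meets the hospitalisation criterion. The exemption then applies because the admission is due to COPD or PD. No other criterion is met.
4. **Reporting (9.2.2).** The result depends on what SAE means in the exemption. The plan uses the term both as one cell of Table 3 and, in the list of criteria, for serious events in general.

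| Reading of SAE in the exemption | Status of the admission | METC timeline in 9.2.2 |
|---|---|---|
| Any serious event | Exempt; falls to the non-serious tier | None: the 7- and 15-day rules apply to SAEs |
| Only the non-device-related cell of Table 3 | Not exempt; a SADE | None stated: SADE is in the section heading, but the timelines name only SAEs |

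Neither reading gives the event an explicit expedited route. Other sections do not supply one. Section 9.2.3 covers device deficiencies. Section 9.3 mentions expedited reporting of SUSARs and an annual list of serious adverse reactions, but sets no time limit for a SADE.

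5. **What remains.** The event stays a recorded AE. Section 8.8 calls for an evaluation of continued participation after an adverse event, serious or not. The suspension trigger in 9.2.2 rests on the frequency and severity of adverse effects and not on SAE status, so the event still counts there.

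**Size.** The documents contain no admission or exacerbation rate, and no share of admissions that might be provoked by a test. Planned exposure can be bounded: 200 COPD participants × 15 weekly tests = 3,000 home 6-minute walk tests at most, before the 25% data loss allowed for in section 4.4. That is a count of tests and says nothing about the number of admissions affected.

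**The case against.** The strongest defence is that the plan's own table already settles the matter. If SAE means only the non-device-related cell, a test-provoked admission is a SADE and was never exempt. That reading is available, and so the conflict with Table 3 is an ambiguity and not a proven contradiction. It does not rescue the reporting, because 9.2.2 attaches its METC timelines to SAEs alone.

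A reader might infer several stronger things that the documents do not support:

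- *That PD and COPD admissions can never be SAEs.* The exemption concerns hospitalisations. An event that "Results in death", threatens life, disables or is otherwise medically important can still qualify under its own criterion.
- *That the signal disappears or goes unassessed for cause.* AEs are recorded and classified by relatedness, Visits 2 to 4 collect adverse events and changes in health status (section 8.3, Table 2), and section 9.1 allows suspension on safety grounds generally. The event is downgraded in the reporting, not erased.
- *That admissions provoked by training sessions are an equal example.* The Summary and section 5 present the physiotherapy as usual care that participants would receive anyway, although the Summary also calls it an intervention. The home walk tests are the clear case.
- *That falls in PD are lost.* The Summary names falls as a main risk of home testing. Such an admission would be exempt only if coded as due to PD. The undefined 'due to' permits that coding, but nothing directs it.

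An exemption for disease-related admissions can also serve a sensible purpose, since it keeps expected events from crowding the reports. That justifies exempting unrelated admissions; it does not justify exempting those caused by the study.

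**Conclusion.** Wrong as written. Sections 9.2.1 and 9.2.2 apply different rules to study-caused worsening, and the status of SADEs is left open. Taken literally, a COPD or PD admission provoked by a home walk test leaves the 15-day METC reports and the SAE listing in the annual progress report, unless it meets another seriousness criterion. It remains an AE and still counts toward suspension.

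The number of admissions affected cannot be estimated from the documents. A reader might multiply an assumed admission rate by the follow-up time, but that would count all COPD admissions. Only provoked ones matter here, and their share is unknown and could be close to zero.

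The conclusion rests on a literal reading of the exemption and on treating the home walk tests as study procedures. It needs no assumed rate.

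**What to change.** Reconcile 9.2.2 with 9.2.1 and Table 3:

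- Limit the exemption to PD or COPD admissions that the investigator judges unrelated to the study device, the walk tests or other study procedures.
- State that the exemption does not apply to SADEs.
- State that SADEs follow the same METC timelines as SAEs.

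This takes a clause in the exemption and a sentence on SADEs. The cost is one relatedness judgement per admission and a few more reports.

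The change does not require unrelated, exempt admissions to be recorded as AEs. Under 9.2.1, worsening of a pre-existing condition that the study did not cause is not an AE, so recording it would be a separate decision that goes beyond that section.

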9.2.3 Device deficiencies, device failures and malfunctions

A device deficiency is defined as an inadequacy of a medical device related to its identity, quality, durability, reliability, safety or performance. This may include malfunctions, use errors, or inadequacy in the information supplied by the manufacturer.

An incident is any malfunction or deterioration in the characteristics and/or performance of a device, as well as any inadequacy in the labeling or the instructions for use which, directly or indirectly,

might lead to or might have led to the death of a patient, or USER or of other persons or to a serious deterioration in their state of health.

Throughout the study, and in conformity with ISO 14155:2020, and Medical device Regulation Regulation (EU) 2017/745, all observed device deficiencies are to be documented by the Investigator and reported to the Manufacturer on Device Deficiency Forms that are included in the study documentation. The investigational device is returned to the Sponsor for analysis if necessary. Instructions for returning the investigational device will be provided by Verily.

The Investigator is responsible for notification of the sponsor within 5 working days.

Device deficiencies that meet the definition for incidents (i.e. any device deficiency or failures that might lead or might have led to a serious adverse event if suitable action had not been taken, or intervention had not been made, or if circumstances had been less fortunate) must be reported to the Verily immediately without delay.

9.3 Annual safety report

In addition to the expedited reporting of SUSARs, the sponsor will submit, once a year throughout the clinical trial, a safety report to the accredited METC, competent authority, and competent authorities of the concerned Member States.

This safety report consists of:

- A list of all suspected (unexpected or expected) serious adverse reactions, along with an aggregated summary table of all reported serious adverse reactions, ordered by organ system, per study; and
- A report concerning the safety of the subjects, consisting of a complete safety analysis and an evaluation of the balance between the efficacy and the harmfulness of the medicine under investigation.

